12.4. Statistical Analyses

Summary tabulations will be provided for disposition, demographic, baseline, efficacy, and safety data as noted in the following sections.

12.4.1. Efficacy Analyses

The primary efficacy analysis will be performed on the mITT population.

12.4.1.1. Primary Endpoint

The primary efficacy endpoint of ORR (proportion of patients who achieve CR or PR) will be analyzed for each arm separately on the mITT population which consists of all enrolled patients who received any study treatment. Estimated ORR with 95% confidence interval (CI) will be summarized for each arm.

12.4.1.2. Secondary Endpoints

- Progression-free survival is defined as time from date of first treatment to the date of first confirmed PD, or death due to any cause, whichever occurs first. Median PFS with 95% CI will be summarized for each treatment arm.
- Overall survival is defined as time to death, from the date of first treatment. Median OS with 95% CI will be summarized for each treatment arm.
- Complete response rate is defined as proportion of patients who achieved a CR. The point estimate and an 95% exact CI of CRR will be provided for each treatment arm.
- Duration of response is defined as the duration of time from first occurrence of response \geq PR until the first date of PD or death due to any cause, whichever occurs first. Median DOR with 95% CI will be summarized for each treatment arm.
- Disease control rate is defined as the percentage of patients who have achieved CR, PR or stable disease. The point estimate and an 95% exact CI of DCR will be provided for each treatment arm.

12.4.2. Safety Analyses

All safety analyses will be performed on the Safety Population, unless otherwise specified and will be presented by actual treatment arm. Details of the analyses will be described in the SAP.

The safety and tolerability of selinexor will be evaluated by means of drug-related AE reports, physical examinations, and laboratory safety evaluations. The grading of the severity of the AEs will be done according to CTCAE, v.5.0. Investigators will provide their assessment as either the AE is related or not related to study drug.

Treatment-emergent AEs, SAEs, AEs of at least Grade 3 in severity, related AEs, and AEs leading to withdrawal of treatment will be summarized by Arm and in the overall safety population.

Treatment-emergent AEs will be those that start or worsen on or after the first day of study treatment, through 30 days after last dose (or the day before initiation of a new anti-neoplastic treatment, whichever occurs first). Related AEs will be those with an Investigator determination of related to study drug.

Laboratory data will be analyzed by summary statistics over time, as well as by shift tables based on severity.

Continual monitoring of safety data will be performed by the independent Data Safety Monitoring Board (DSMB). Adverse events and concomitant medications will be coded according to medical dictionary for regulatory activities (MedDRA) and WHO Drug, respectively.

12.4.2.1. Adverse Events

Adverse events will be coded using the MedDRA and displayed in tables and listings using MedDRA system organ class (SOC) and preferred term (PT).

In those instances where the AE only has a partial date recorded, the AE will be assessed using the available date information to determine if it is treatment emergent. For AEs in which the date is completely missing, the AE will be assumed to be treatment emergent. No formal hypothesis-testing of AE incidence rates will be performed.

Adverse events will be summarized by patient incidence rates; therefore, in any tabulation, a patient contributes only once to the count for a given AE (by PT). The number and percentage of patients with any TEAE will be summarized for each cohort, classified by SOC and PT. The number and percentage of patients with TEAEs assessed by the Investigator as related to treatment will also be tabulated. The number and percentage of patients with any Grade ≥ 3 TEAE will be tabulated in the same manner.

In the event a patient experience repeat episodes of the same AE, then the event with the highest severity and/or strongest causal relationship to treatment will be used for purposes of tabulations.

SAEs will be summarized in the same manner as TEAEs.

All AEs (treatment emergent and post-treatment) will be listed in by-patient data listings, classified by cohort, patient, and day on study. In addition, separate by patient listings will be provided for the following: patient deaths; serious AEs; and AEs leading to withdrawal.

12.4.2.2. Laboratory Data

Clinical laboratory values will be expressed using SI units.

For each cohort, the actual value and change from baseline (Day 1, prior to the first administration of study drug) to each on study evaluation will be summarized for each clinical laboratory parameter, including hematology, and clinical chemistry. In the event of repeat values, the last non-missing value per study day/time will be used. In the event that Day 1 data are unavailable for a given patient/parameter, the screening value will substitute as the baseline value.

Severity of select clinical lab measures will be determined using CTCAE criteria (e.g., those measures that have a corresponding CTCAE grade classification). Labs with CTCAE Grades ≥ 3 will be presented in a data listing. Shift tables that present changes from baseline to worst on-study and baseline to last on-study values relative to CTCAE classification ranges will be produced.

12.4.2.3. Vital Signs and Physical Examinations

The actual value and change from baseline (Day 1, prior to the first administration of study treatment) to each on study evaluation will be summarized for vital signs.

By-patient listings of vital sign measurements will be presented in data listings.

Abnormal physical examination results at screening, and abnormal physical examination results (AEs) during the study, will be summarized. All physical examination findings will be presented in by-patient data listings.

12.4.2.4. Concomitant Medications

The use of concomitant medications will be included in by-patient data listings.

13. SUPPORTING DOCUMENTATION AND OPERATIONAL CONSIDERATIONS

13.1. Ethical and Administrative Obligations

13.1.1. Regulatory and Ethical Considerations

This clinical study was designed and shall be implemented and reported in accordance with the International Council for Harmonisation (ICH) Harmonized Tripartite Guidelines for Good Clinical Practice, with applicable local regulations (including European Directive 2001/20/EC and US Code of Federal Regulations (CFR) Title 21), and with the ethical principles that originate from the Declaration of Helsinki.

The protocol and the proposed ICF(s) must be reviewed and approved by a properly constituted IRB/IEC before study start. Prior to study start, the Investigator is required to sign a protocol signature page confirming his/her agreement to conduct the study in accordance with these documents and all of the instructions and procedures found in this protocol and to give access to all relevant data and records to Karyopharm monitors, auditors, designated agents of Karyopharm, IRBs/IECs, and regulatory authorities as required.

Any amendments to the protocol will require IRB/IEC approval before implementation of changes made to the study design, except for changes necessary to eliminate an immediate hazard to study patients.

13.1.2. Responsibilities of the Investigator and Good Clinical Practice

The investigator will be responsible for the following:

- Providing written summaries of the status of the study to the IRB/IEC annually or more frequently in accordance with the requirements, policies, and procedures established by the IRB/IEC
- Notifying the IRB/IEC of SAEs or other significant safety findings as required by IRB/IEC procedures
- Providing oversight of the conduct of the study at the site and adherence to requirements of 21 CFR, ICH guidelines, the IRB/IEC, European regulation 536/2014 for clinical studies (if applicable), and all other applicable local regulations

13.2. Financial Disclosure

Investigators and sub-investigators will provide the sponsor with sufficient, accurate financial information as requested to allow the sponsor to submit complete and accurate financial certification or disclosure statements to the appropriate regulatory authorities. Investigators are responsible for providing information on financial interests during the course of the study and for 1 year after completion of the study.

- A copy of the ICF(s) must be provided to the patient or the patient's legally authorized representative.

Patients will be told that they are free to refuse to participate and may withdraw their consent at any time and for any reason during the storage period. If required by local regulations, in addition to the

primary ICF, there will be a separate form for female partners of participating male patients who are sexually active and accept risks.

13.4. Data Collection and Management

13.4.1. Data Confidentiality

The Investigator must ensure anonymity of the patients. Patients will be assigned a unique identifier by the Karyopharm. Signed ICFs and patient enrollment logs must be kept strictly confidential to enable patient identification at the site.

Any patient records or datasets that are transferred to Karyopharm will contain the identifier only; patient names or any information which would make the patient identifiable will not be transferred.

Information about study patients will be kept confidential and managed under the applicable laws and regulations. Those regulations require a signed patient authorization informing the patient of the following:

- What protected health information (PHI) will be collected from patients in this study
- Who will have access to that information and why?
- Who will use or disclose that information?
- The rights of a research patient to revoke their authorization for use of their PHI.

In the event that a patient revokes authorization to collect or use PHI, the Investigator, by regulation, retains the ability to use all information collected prior to the revocation of patient authorization. For patients that have revoked authorization to collect or use PHI, attempts should be made to obtain permission to collect follow-up safety information (e.g., has the patient experienced any new or worsened AEs) at the end of their scheduled study period.

The data collection system for this study uses built-in security features to encrypt all data for transmission in both directions, preventing unauthorized access to confidential patient information. Access to the system will be controlled by a sequence of individually assigned user identification codes and passwords, made available only to authorized personnel who have completed prerequisite training.

13.4.2. Data Collection

Data collection is the responsibility of the clinical study staff at the site, under the supervision of the site Investigator. The study eCRF is the primary data collection instrument for the study. The Investigator should ensure the accuracy, completeness, legibility, and timeliness of the data reported in the eCRFs and all other required reports. Data reported on the eCRF that are derived from source documents should be consistent with the source documents or the discrepancies should be explained. All data requested on the eCRF must be recorded. Any missing data must be explained. An audit trail will be maintained by the eCRF system.

13.4.3. Site Monitoring

Before study initiation, Karyopharm personnel (or designated contract research organization [CRO]) will review the protocol with the Investigators and their staff (e.g., at a site initiation visit). During the study, the monitor will visit the site regularly to check the completeness of patient

records, accuracy of entries on the CRFs, adherence to the protocol and to GCP, progress of enrollment, and to ensure that study treatment is being stored, dispensed, and accounted for according to specifications. Key study personnel must be available to assist the monitor during these visits.

The Investigator must maintain source documents for each patient in the study, consisting of case and visit notes (hospital or clinic medical records) containing demographic and medical information, laboratory data, and the results of any other tests or assessments. All information recorded on CRFs must be traceable to source documents in the patient's file. The Investigator must also keep the original signed ICF (a signed copy is given to the patient).

The Investigator must give the monitor access to all relevant source documents to confirm their consistency with the CRF entries. Karyopharm monitoring standards require full verification for the presence of informed consent, adherence to the inclusion/exclusion criteria and documentation of SAEs. Additional checks of the consistency of the source data with the CRFs are performed according to the study-specific monitoring plan.

13.4.4. Data Captures

This study will utilize electronic data capture (EDC), the designated clinical site staff will enter the data required by the protocol into the eCRF. The eCRFs will be constructed using fully validated secure web-enabled software that conforms to 21 CFR Part 11 requirements. Clinical site staff will not be given access to the EDC system until they have been trained. Automatic validation programs check for data discrepancies in the eCRFs and allow modification or verification of the entered data by the Investigator staff.

The Investigator is responsible for assuring that the data entered into the eCRF is complete and accurate, and that entry and updates are performed in a timely manner.

Concomitant treatments and prior medications entered into the database will be coded using the WHO Drug Reference List, which employs the Anatomical Therapeutic Chemical (ATC) classification system. Medical history/current medical conditions and AEs will be coded using the MedDRA terminology.

13.4.5. Database Management and Quality Control

Karyopharm personnel (or designated CRO) will review the eCRF data entered by investigational staff for completeness and accuracy. Electronic data queries stating the nature of the problem and requesting clarification will be created for discrepancies and missing values and sent to the investigational site via the EDC system. Designated Investigator site staff are required to respond promptly to queries and to make any necessary changes to the data.

At the conclusion of the study, after discrepancies and missing values have been completed and the data have been verified to be complete and accurate, the database will be declared locked.

For EDC studies, after database lock, the Investigator will receive a CD-ROM or paper copies of the patient data for archiving at the investigational site.

13.5. Structure of Committees

13.5.1. Data Safety Monitoring Board

An independent DSMB will be established and will review the safety of study treatment and any SAEs that occur during the study. Details on how the DSMB will review safety and response data are provided in the DSMB Charter.

The DSMB will be composed of at least two oncologists (at least one of whom specializes in melanoma) and a statistician. Following their initial meeting, the DSMB will meet approximately every 6 months to review clinical data and provide recommendations to the Sponsor on whether the study should continue. The DSMB may also meet more frequently, if needed.

13.6. Dissemination of Clinical Study Data

Results from the study (including demographics, baseline characteristics, primary and secondary endpoints) will be posted in a publicly accessible database (such as ClinicalTrials.gov or EudraCT) in accordance with applicable laws, regulations, and/or guidelines.

In addition, upon study completion and finalization of the clinical study report, the results of this study may be submitted for publication in a peer-reviewed journal or presented at a scientific/biomedical conference.

13.7. Source Documents

Each participating site will maintain appropriate medical and research records for this study, in compliance with Section 4.9 of the ICH E6 GCP, and regulatory and institutional requirements for the protection of confidentiality of patients. As part of participating in a Karyopharm-sponsored study, each site will permit authorized representatives of Karyopharm and regulatory agencies to examine (and when required by applicable law, to copy) clinical records for the purposes of quality assurance reviews, audits and evaluation of the study safety and progress.

Source data are all information, original records of clinical findings, observations, or other activities in a clinical study necessary for the reconstruction and evaluation of the study. Examples of these original documents and data records include, but are not limited to, hospital records, clinical and office charts, laboratory notes, memoranda, patients' diaries or evaluation checklists, pharmacy dispensing records, recorded data from automated instruments, copies or transcriptions certified after verification as being accurate and complete, microfiches, photographic negatives, microfilm or magnetic media, x-rays, and patient files and records kept at the pharmacy, at the laboratories, and medico-technical departments involved in the clinical study.

The Investigator/institution should maintain the study documents as specified in Essential Documents for the Conduct of a Clinical Trial (ICH E6 Section 8) and as required by applicable regulations and/or guidelines. The Investigator/institution should take measures to prevent accidental or premature destruction of these documents.

Essential documents (written and electronic) should be retained for a period of not less than fifteen (15) years from the completion of the clinical study unless Karyopharm provides written permission to dispose of them or, requires their retention for an additional period of time because of applicable laws, regulations and/or guidelines.

13.8. Study and Site Closure

The Sponsor or designee reserves the right to close the study site or terminate the study at any time for any reason at the sole discretion of the Sponsor. Study sites will be closed upon study completion. A study site is considered closed when all required documents and study supplies have been collected and a study-site closure visit has been performed.

The Investigator may initiate study-site closure at any time, provided there is reasonable cause and sufficient notice is given in advance of the intended termination.

Reasons for the early closure of a study site by the Sponsor or Investigator may include but are not limited to:

- Failure of the Investigator to comply with the protocol, the requirements of the IRB/IEC or local health authorities, the Sponsor's procedures, or GCP guidelines
- Inadequate recruitment of patients by the Investigator
- Discontinuation of further study treatment development

13.9. Publication Policy

The results of this study may be published or presented at scientific meetings. If this is foreseen, the investigator agrees to submit all manuscripts or abstracts to the sponsor before submission. This allows the sponsor to protect proprietary information and to provide comments.

The sponsor will comply with the requirements for publication of study results. In accordance with standard editorial and ethical practice, the sponsor will generally support publication of multicenter studies only in their entirety and not as individual site data. In this case, a coordinating investigator will be designated by mutual agreement.

Authorship will be determined by mutual agreement and in line with International Committee of Medical Journal Editors authorship requirements.

APPENDIX 1. RECIST VERSION 1.1

(Modified from [Eisenhauer 2009](#))

All patients will have their BEST RESPONSE on study classified as outlined below:

Complete Response (CR)

Disappearance of all target lesions. Any pathological lymph nodes (whether target or non target) must have reduction in the short axis to <10mm.

Partial Response (PR)

At least a 30% decrease in the sum of diameters of target lesions, taking as reference the baseline sum diameters.

Stable Disease (SD)

Steady state of disease. Neither sufficient shrinkage to qualify for PR nor sufficient increase to qualify for PD.

Progressive Disease (PD)

At least a 20% increase in the sum of diameters of measured lesions taking as references the smallest sum of diameters recorded since the treatment started. In addition to the relative increase of 20%, the sum must also demonstrate an absolute increase of at least 5 mm. Appearance of one or more new lesions will also constitute progressive disease.

Response Duration

Response duration will be measured from the time measurement criteria for CR/PR (whichever is first recorded) are first met until the first date that recurrent or progressive disease is objectively documented, taking as reference the smallest measurements recorded since the treatment started.

Stable Disease Duration

Stable disease duration will be measured from the time of start of therapy until the criteria for progression are met, taking as reference the smallest measurements recorded since the treatment started.

Evaluation of Best Overall Response – Patient with Target (\pm non-target) disease

Target lesions	Non-Target lesions	New Lesions	Overall response
CR	CR	No	CR
CR	Non-CR-Non-PD	No	PR
CR	NE	No	PR
PR	Non-PD/or not all evaluated	No	PR
SD	Non-PD/or not all evaluated	No	SD
Not all evaluated	Non-PD	No	NE

Target lesions	Non-Target lesions	New Lesions	Overall response
PD	Any	Yes or No	PD
Any	PD	Yes or No	PD
Any	Any	Yes	PD

CR: complete response; NE: non-evaluable; PD: progressive disease; PR: partial response; SD: stable disease.

Evaluation of Best Overall Response – Patient with Non-Target Disease

Non-Target lesions	New Lesions	Overall response
CR	No	CR
Non-CR-Non-PD	No	Non-CR/Non-PD ¹
Not all evaluated	No	NE
Unequivocal PD	Yes or No	PD
Any	Yes	PD

CR: complete response; NE: non-evaluable; PD: progressive disease; PR: partial response.

Note: Patients with a global deterioration of health status requiring discontinuation of treatment without objective evidence of disease progression at that time should be reported as “*symptomatic deterioration*”. Every effort should be made to document the objective progression even after discontinuation of treatment.

Method of Measurement

The same method of assessment and the same technique should be used to characterize each identified and reported lesion at baseline and during follow-up.

Clinical Lesions

Clinical lesions will only be considered measurable when they are superficial (e.g., skin nodules, palpable lymph nodes). For the case of skin lesions, documentation by color photography including a ruler to estimate the size of the lesion is recommended.

CT, MRI

CT and MRI might be the best currently available and reproducible methods to measure target lesions selected for response assessment. Conventional CT and MRI should be performed with cuts of 10 mm or less in slice thickness contiguously. Spiral CT should be performed using a 5 mm contiguous reconstruction algorithm. This applies to the chest, abdomen and pelvis. Head & neck and extremities usually require specific protocols.

Cytology, Histology

These techniques can be used to differentiate between PR and CR in rare cases (for example, residual lesions in tumor types such as germ cell tumors, where known residual benign tumors can remain). The cytological confirmation of the neoplastic origin of any effusion that appears or worsens during treatment when the measurable tumor has met criteria for response or stable disease

is mandatory to differentiate between response or stable disease (an effusion may be an adverse drug reaction of the treatment) and PD.

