10.3. Efficacy Assessments

10.3.1. Response criteria

Computed Tomography (CT) or Magnetic Resonance Imaging (MRI)

Disease response is based on tumor measurement using CT scans or, MRI. Scans will be performed at Screening (Day -28 to Day -1) and every 9 weeks for 6 months, then every 3 months thereafter until confirmed PD, death or consent withdrawal occurs. Scans at the EoT visit should be performed for patients who discontinue for reasons other than documented PD, if previous imaging was more than 6 weeks old. The same scan modality should be used for all assessments.

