4.3. Secondary Efficacy Endpoints

4.3.1. Definition of Secondary Efficacy Endpoints

Table 4-1 are the secondary efficacy endpoints:

Table 4-1 Efficacy Endpoints and Definitions

Endpoint	Definition
Secondary Endpoints	
Progression-free survival (PFS)	Duration of time from date of first study treatment until the first date that PD assessed by RECIST 1.1 is objectively documented or death due to any cause. Refer to Table 4-2 for details on PFS outcome status (PFS event vs. censored) and censoring definitions.
Overall survival (OS)	Duration from the date of first study treatment until death due to any cause. If death event did not occur during the follow-up period, the patient is censored at the date of discontinuation from the study (i.e. withdrawal of consent), or date of last participating visit (e.g., a telephone contact with patient status being alive) on or before database cutoff date, whichever occurs first.
Complete response rate (CRR)	Proportion of patients who achieved a CR per RECIST 1.1
Duration of response (DOR)	Duration of time from first meeting CR or PR measurement criteria (whichever occurs first) until the first date that PD recurrence is objectively

	documented or death due to any cause. Responses are assessed per RECIST 1.1.
	Refer to Table 4-2 or details on the outcome and censoring definitions.
Disease control rate (DCR)	Proportion of patients who have a response of CR, PR, or SD ≥ 12 weeks. Responses are assessed per RECIST 1.1.

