4.3.2.2. Analyses of Time to Event Secondary Endpoints

[figure not shown]
For each time to event secondary endpoint (PFS, OS and DOR), the number of patients with events, number of patients censored, estimates and 95% CI for the median of event time will be presented by treatment group.

[figure not shown]
Time-to-event will be plotted for each treatment group using the Kaplan-Meier method. The plot will include the number of patients at risk for each treatment group over time.

Table 4-2 PFS and DOR Outcome and Censoring Definitions

#	Situation	Date of event or censoring	Outcome
1	No baseline disease assessment	Date of first treatment	Censored
2	No adequate post-baseline disease status assessment unless death occurs prior to first post-baseline assessment	Date of first treatment	Censored
3	Documented PD without missing 2 or more consecutive assessments	Date of PD	Event
4	Death before documented PD and without missing 2 or more consecutive assessments	Date of death	Event
5	 No documented PD or death on or before Database cut Withdrawal of informed consent Lost to follow-up Date of discontinuation from treatment + 30 days Two or more consecutive missing assessments and the disease assessment result after the gap is PD¹ Start of new antineoplastic therapy, whichever occurs first 	Date of last adequate disease assessment prior to the events listed in the left column	Censored

^{1.} If disease assessment results after 2 or more consecutive missing assessments were not PD, the disease assessment gap will be ignored.

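### SAP Table 4-2 censors patients who stop for symptomatic deterioration, and no sensitivity analysis tests this, so PFS and DOR may be overstated

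*Protocol*

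**What the plan says.** **Protocol, Appendix 1 (note).** "Patients with a global deterioration of health status requiring discontinuation of treatment without objective evidence of disease progression at that time" are to be reported as symptomatic deterioration, a category separate from PD. The note goes on: "Every effort should be made to document the objective progression even after discontinuation of treatment".

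**SAP 4.3.1, Table 4-1.** PFS runs from first study treatment "until the first date that PD assessed by RECIST 1.1 is objectively documented or death due to any cause". DOR ends on the same kinds of event.

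**SAP 4.3.2.2, Table 4-2.** Row 3 makes documented PD an event. Row 4 does the same for "Death before documented PD and without missing 2 or more consecutive assessments". Row 5 covers patients with neither by the first of several triggers, among them "Date of discontinuation from treatment + 30 days" and "Start of new antineoplastic therapy, whichever occurs first". Their censoring date is the "Date of last adequate disease assessment prior to the events listed in the left column". No row mentions symptomatic deterioration.

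**Imaging around discontinuation.** Protocol 10.3.1 asks for an end-of-treatment (EoT) scan after discontinuation for reasons other than PD "if previous imaging was more than 6 weeks old". The synopsis sets the limit at 3 weeks and allows up to 28 days for the scan. Under Protocol 6.2, PFS follow-up then continues about every 3 months until PD, death or new therapy.

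**Supportive analyses.** SAP 3.1.2 and 4.1 change the analysis population only, not the event or censoring rules.

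**The concern.** Kaplan-Meier assumes that a censored patient has the same later risk as those still under observation. A patient who leaves treatment because of failing health probably does not. If the tumour is the cause, censoring at the last scan removes a patient close to progression and leaves the fitter ones in the risk set. The error then goes one way, upward, and does not shrink as the sample grows.

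The 30-day trigger adds to this. It applies with or without new therapy. It also appears to cut off the follow-up that the protocol itself arranges: the 3-monthly PFS visits and the search for objective progression requested in Appendix 1.

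At stake is how the secondary results are read. The arms have no concurrent control, and the protocol cites a median PFS of 4.2 months from a study of pembrolizumab with lenvatinib after progression on anti-PD-1 therapy. Readers are likely to set this trial's PFS beside that figure.

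**Working it through.** The documents give no event count or power for PFS, so there is no figure to reproduce. The check has two parts.

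**1. What happens to a patient who stops for symptomatic deterioration**

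| Course after stopping | Result under Table 4-2 |
|---|---|
| EoT scan within 28 days shows PD, no new therapy yet | Event (row 3) |
| Death before any trigger, fewer than two missed assessments | Event (row 4) |
| New therapy before documented PD | Censored at last adequate scan |
| No EoT scan required, or none showing PD; PD found at 3-monthly follow-up | Day 30 comes first: censored at last adequate scan |

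The last line is a literal reading. Row 3 alone has no time limit, but row 5 applies to anyone without PD or death by the earliest trigger, and the first 3-monthly visit normally falls after day 30.

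**2. Illustrative size**

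Inputs from the documents: median 4.2 months (Protocol 4.2); scans at Weeks 9, 18 and 27 (every 9 weeks for 6 months, Protocol 10.3.1); EoT scan limits of 6 weeks (10.3.1) and 3 weeks (synopsis); EoT visit up to 28 days after discontinuation.

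Assumptions: exponential failure times; a share f of failures presents as symptomatic deterioration; every such case is true progression; no deaths; a required EoT scan shows PD before a trigger applies.

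- The median is 4.2 × 4.348 = 18.26 weeks. Nine-week survival is 2^(−9/18.26) = 0.7106. With deterioration as an event, Week-27 PFS is 0.7106³ = 35.9%.
- Patients who deteriorate within *a* weeks of a scan need no EoT scan and are censored back at that scan. The chance of failing in those weeks is p(a) = 1 − 2^(−a/18.26), so p(9) = 0.2894, p(6) = 0.2037, p(3) = 0.1076, p(2) = 0.0731 and p(0) = 0.
- Each 9-week Kaplan-Meier factor becomes 0.7106 / (1 − f·p(a)), and Week-27 PFS is its cube. For f = 20% and a = 6: 0.7106 / (1 − 0.2 × 0.2037) = 0.7408, and the cube is 40.7%.
- Upper end of each range: scan age judged on the day of deterioration (a = 6 or 3).
- Lower end: scan age judged at an EoT visit 4 weeks later, so a = 6 − 4 = 2 under the 6-week rule and 0 under the 3-week rule. PD is then dated up to 4 weeks late, which adds f × [S(23) − S(27)] = f × (0.418 − 0.359), or 0.6, 1.2 and 1.8 points.

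| f | Deterioration an event | 3-week rule | 6-week rule | No case caught (a = 9) |
|---|---|---|---|---|
| 10% | 35.9% | 36.5–37.1% | 37.3–38.2% | 39.2% |
| 20% | 35.9% | 37.1–38.3% | 38.7–40.7% | 42.9% |
| 30% | 35.9% | 37.7–39.6% | 40.1–43.4% | 47.1% |

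In round figures, with up to a point of slack for how an EoT finding is dated, this is about 36–37%, 37–38% and 38–40% under the 3-week rule, and 37–38%, 38–41% and 40–43% under the 6-week rule.

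A simulation of 20-patient arms with an underlying median of 4.2 or 8.8 months (both medians are cited in the protocol) agrees. At f = 10%, 20% and 30% the 6-month PFS rate rises by about 3, 6–7 and 10–11 points if no case is caught, and by about 2, 3 and 5–6 points if half are. The observed median moves by zero or about one scan interval. No calculation was made for DOR; it uses the same table, in responders only.

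**The case against.** **Safeguards exist.** Appendix 1 asks for objective progression to be sought after treatment stops, an EoT scan is planned for many of these patients, and death before a trigger is an event. A reader might infer that every clinically worsening patient goes unscanned and is censored. The documents do not support that: the Appendix 1 category means no objective evidence of PD, not no scan. What stands against the safeguards is that the EoT scan is conditional, and that later findings generally fall beyond day 30.

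**The largest figures are not the expected ones.** A reader might take 39%, 43% and 47% as the effect. Those require that no EoT scan ever shows PD, which contradicts the scan rules; they are an upper bound. Medians of 4.2/(1 − f) = 4.7, 5.3 and 6.0 months need the same assumption and also ignore scan timing.

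**Deterioration may be toxicity.** Protocol 4.5 lists fatigue, anorexia and weight loss among selinexor's effects. Counting such declines as progression would understate PFS. This stands, and is why the alternative belongs in a sensitivity analysis.

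**The endpoint is secondary and imprecise.** With 20 patients, a 36% rate has a standard error of about √(0.36 × 0.64/20) = 11 points, larger than the illustrated bias under either scan rule. The cited study's censoring rules are not given, so an unfair comparison is not shown. Both points limit the importance; neither removes a bias of known direction.

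**Part of the remedy may already exist.** Protocol 9.1 records the reason for discontinuation, SAP 3.1 tabulates it, and SAP 4.3.2.2 reports the total censored. The eCRF, SAP 1.4 and Table 4-3 are not in the available text, and their absence is not held against the plan.

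**Conclusion.** The point holds as a modest one. Symptomatic deterioration is a protocol category that the SAP leaves out of its PFS and DOR rules. Row 5 censors these patients at the last adequate scan through either of two triggers, and no analysis in the available text varies that. If the decline is tumour-driven, PFS and DOR may be overstated. Under the stated assumptions the gain in Week-27 PFS is about 1–2, 2–5 and 4–7 points for f = 10%, 20% and 30% with the 6-week scan rule, and at most about 4 points with the 3-week rule. The documents do not give f, the share caught by EoT scans or the share due to toxicity, so the true size cannot be fixed from them.

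A reader might infer that PFS is certainly overstated, or that new therapy alone drives the censoring. Neither follows: deaths before a trigger count as events, some declines will not be progression, and the 30-day trigger works without new therapy. The primary endpoint, ORR, does not use Table 4-2.

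**What to change.** Keep Table 4-2 for the main analysis. Before database lock, add to SAP 4.3.2.2:

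- **(a)** A sensitivity Kaplan-Meier estimate of PFS and DOR per arm in which symptomatic deterioration, or start of new antineoplastic therapy before documented PD, is an event on its date. State that the 30-day trigger does not pre-empt these events; otherwise new therapy begun after day 30 could never count.
- **(b)** A second sensitivity estimate without the discontinuation plus 30 days trigger, so that PD or death found in planned follow-up counts.
- **(c)** The number of patients censored for each reason, per arm.

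Make sure symptomatic deterioration can be identified from the discontinuation reason in the eCRF. Reconcile the EoT scan rules in the synopsis and Protocol 10.3.1, since they decide how many of these patients are imaged.

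The cost is one or two extra tables per endpoint and, if it is missing, one eCRF response option. Estimate (a) may count some toxicity-driven declines as progression, so it stays a sensitivity analysis. If few patients are affected, the estimates will agree and support the main result.
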